Specific Aim 1: Compare the short-term and long-term impact of the active intervention and control condition on healthy lifestyle behaviors (PA and nutritional patterns) associated with chronic disease risk reduction. Hypothesis 1: Participants in the active intervention whose levels of PA and F/V consumption are meeting national recommendations at baseline (BL) will be more likely to maintain these at 4 and 8 months than participants in the control group whose levels fall within national recommendations at baseline. Hypothesis 2: Participants in the active intervention whose levels of PA and F/V consumption not meeting national recommendations at BL will have greater improvement in PA and F/V consumption at 4 and 8 months compared to participants in the control group whose levels are not meeting national recommendations at BL. Specific Aim 2 Compare the short-term and long-term impact of the active intervention and control condition on anthropometric (weight and waist circumference) and biological (blood pressure (BP), HbA1c, and lipids) chronic disease risk factors. Hypothesis 1: Participants in the active intervention whose anthropometric and biological measures are within normal ranges at BL will be more likely to maintain these ranges throughout the period of the study than participants in the control group whose levels are within normal ranges at BL. Hypothesis 2: Participants in the active intervention whose anthropometric and biological measures outside of normal ranges at BL will have greater improvement in these measures at 4 and 8 months than participants in the control group whose levels are outside of normal ranges at BL.

Study Design: Describe the study design (e.g., single/double blind, parallel, crossover, etc.). Indicate whether or not the subjects will receive placebo medication at some point in the research procedures. Also, indicate whether or not the subjects will be randomized in this study. You may reference sponsor's protocol pages and attach as an appendix in the E-IRB "Additional Information" section. (Including the study design table from a sponsor's protocol is helpful to IRB members.)

Community-Based Participatory Research: If you are conducting community-based participatory research (CBPR), describe strategies for involvement of community members in the design and implementation of the study, and dissemination of results from the study.

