The sample population consists of a convenience sample that is participating in a pilot study. This study will focus on nonpregnant healthy adult (ages 18+) community members who walk the Tanglewood Trail on Saturdays, June-September 2018 and at Letcher County Recreation Center October 2018 – February 2019. Any interested community members who are 18 years or older, nonpregnant and able to voluntarily give their consent are welcome to join the study. Seventy-five participants will be recruited to participate in this project in Whitesburg ("walking group"), and seventy-five control participants will be recruited in Harlan ("control group"), who will only receive monthly nutrition education via e-mail or home mail. An information session for any potentially interested individuals will be held by the UK program manager with the help of the community leader following IRB approval. The 75 walking group participants will meet at the Housing Authority at a designated time each Saturday. When they arrive, they will be signed in by a community leader and receive a farmer's market voucher (see attached) for \$10. They will walk as a group to the farmer's market and hand their voucher to the market manager, who will give them \$10 in tokens to purchase fruits and vegetables at the market. The voucher will have two sides: one side will ask participants to check off what fruits and vegetables they ate over the past week, the second side will ask how participants used what they purchased at the market last week (ie. How much was eaten fresh vs. preserved) and how many steps they took over the past week, tracked using a pedometer provided at the baseline measurements in May 2018. They will turn the filled-out voucher in as they leave the market. During the meal preparation portion of the study, participants will complete weekly meal evaluation sheets. The walking group will receive 1) Education - nutrition education weekly via a combination of nutrition posts on Facebook (2/mo June – Sept), recipe and phytonutrient cards that includes a video recipe demonstration (1/mo), and recipe samples with cards (1/mo). Post-farmer's market: 1 weekly recipe demonstration (YouTube and offered live), recipes with nutrition/phytonutrient information to accompany meals (Oct – Jan); 2) Vouchers- weekly \$10 farmer's market vouchers (June – Sept), weekly \$20 healthy meal vouchers (Oct – Jan); 3) PA - 1 day/week community walk along Tanglewood Trail (June-Sept) and admission to Recreation Center (Oct – Jan), and 4) Activity trackers - a 3DTriSport pedometer. The 75 control group participants will receive monthly nutrition education via their choice of e-mail or home mail. Nutrition education will focus on phytonutrients, the importance of fruit and vegetable intake, how these factors might protect them from environmental pollutants, and healthy cooking. This nutrition education will also be provided to walking group participants via Facebook. Walking group participants will also have access to monthly Farmer's Market samples of Plate it Up Kentucky Proud recipes and recipe cards. No participants will receive medications – neither real nor placebo. Data for both the walking group and control group will be a time series collection of blood pressure, finger-stick total cholesterol, LDL, HDL, triglycerides, hemoglobin A1c (cardiocheck meter), height, weight, waist circumference, carotenoid status (carotenoid RS, which is a non-invasive instrument that is a reliable indicator of fruit and vegetable intake (see attached), Newest Vital Sign (NVS) rapid screening test for health literacy, and a survey (see attached). Measurements will be taken and surveys collected three times – baseline data will be collected in May 2018, mid-point data collected late September/early October 2018, and follow-up data collected in February 2019. Only walking group participants will receive pedometers and report weekly steps to the community leader at the Farmer's Market (June through September) or CANES Kitchen (October through February). Finger stick tests will be conducted by University of Kentucky employees who have completed all necessary biohazard training (see attached IBC approval and certificates of completion). Lysol wipes will be available to wipe down equipment as needed. Hand sanitizer will be provided to each researcher to use between glove changes. Gloves will be changed between each participant. Heat packets will be available for participants with cold hands to make the finger stick go faster and easier. Band-Aids will be provided after each stick. Lancets will be used to take the finger stick and all materials will be disposed of in sharps containers. All sharps containers will remain sealed until the research team returns to the University of Kentucky that same day to dispose of the sharps containers. Additionally, focus groups with walking group participants will be conducted in October 2018 and February 2019. Questions for the focus groups will be formulated out of 5-10 informant interviews conducted in July (with each interview lasting approximately 30 minutes – 1 hour). Participants for both interviews and focus groups will be recruited with the help of the market manager and community leader, and all participants will be informed that they are participating in the interviews and/or focus groups for research purposes and sign a consent form. Questions asked will assess program use, attitude/behavior change over the course of the program, social capital, and social cohesion.

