[name], University of Kentucky. An electronic document containing participant name and code will be generated and stored on a password protected computer. Following the collection of post-survey data and coding of the post-survey data the electronic document containing the names and codes will be deleted. To minimize risk of identification the consent forms will be removed from the survey and the survey will have a code written on it. The consent forms, shopping cards and surveys will not be stored together, but both will be in a locked drawer. The information collected will be used to assess whether walking 1 mile to the farmer's market and spending approximately \$10 at the market (June through September) and receiving a healthy prepared meal once per week (October through February) improves physical activity, fruit and vegetable intake, community engagement, group cohesion, and chronic disease-related biomarkers (i.e. cholesterol, A1c, etc).

Confidentiality: Specify where the data/specimens will be stored and how the researcher will protect both the data and/or specimens with respect to privacy and confidentiality. Address physical security measures (e.g., locked facility, limited access); data security (e.g., password-protection, data encryption); safeguards to protect identifiable research information (e.g., coding, links, certificate of confidentiality); and procedures employed when sharing material or data, (e.g., honest broker (if applicable), written agreement with recipient not to re-identify). If you plan to procure, store, and/or share material (tissue/specimens/data) expressly for use in current or future research, describe measures that you will take to secure and safeguard confidentiality and privacy.

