If yes, check below all that apply and attach the applicable document(s): [?](#)

- HIPAA De-identification Certification Form
- HIPAA Waiver of Authorization

[Attachments](#)

STATISTICAL ANALYSIS PLAN

This study will recruit approximately 150 participants, who will be divided into walking or non-walking groups to assess dietary behavior. Outcomes will compare the change in fruit and vegetable intake, health and exercise at baseline, 4 months and 8 months using survey metrics. Significance will be determined using a two-way ANOVA with a post-hoc Tukey's t-test; $p<0.05$.

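### Arm and community coincide without randomisation, yet the SAP plans a two-way ANOVA with no covariates and sets no limit on reading the result as a programme effect

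*Combined protocol and SAP*

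**What the plan says.** The SAP has three sentences. On the groups: "This study will recruit approximately 150 participants, who will be divided into walking or non-walking groups to assess dietary behavior". On the outcome: "Outcomes will compare the change in fruit and vegetable intake, health and exercise at baseline, 4 months and 8 months using survey metrics". On the test: "Significance will be determined using a two-way ANOVA with a post-hoc Tukey's t-test", at p<0.05. It names no ANOVA factors, deciding term, covariates, treatment of repeated visits, or limit on interpretation.

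The protocol shows how the groups arise. Study Design says "The sample population consists of a convenience sample that is participating in a pilot study". It continues "Seventy-five participants will be recruited to participate in this project in Whitesburg" for the walking group and places the 75 controls in Harlan. Subject Recruitment Methods & Privacy gives the control arm its own community leader in Harlan County. It says recruitment and consent will follow a similar procedure, and Study Population applies the same eligibility criteria to both arms. No randomisation is described in the available text.

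On the intended reading, both specific aims in Objectives compare the impact of intervention and control. The hypotheses are that walkers "will have greater improvement in PA and F/V consumption at 4 and 8 months compared to participants in the control group" and "will be more likely to maintain these at 4 and 8 months than participants in the control group". Research Materials, Records and Privacy says the data will be used to assess whether the programme "improves physical activity, fruit and vegetable intake, community engagement, group cohesion, and chronic disease-related biomarkers".

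**The concern.** A reader of the SAP alone could take *divided* to mean allocation from a single pool. In fact a participant's arm is fixed by where that person was recruited, with one community per arm and volunteers in each. The walking arm also grows out of a group that formed by itself in 2016, and its expected size is based on 2017 walking numbers, so its selection is unlikely to match that of the Harlan arm.

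In such a design a difference between arms can come from the programme, from who volunteered, or from what happened in the two communities over the eight months. With no adjustment planned and no caution stated, p<0.05 could be reported as evidence that the programme works when the comparison cannot show that by itself.

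**Working it through.** **Inputs from the documents.** 75 walkers + 75 controls = 150, which agrees with the SAP's approximate total. There are three visits (baseline, 4 and 8 months) and a 0.05 threshold, taken here as two-sided because sidedness is not stated. The documents give no effect size, SD, within-person correlation or community difference, so every such value below is an assumption.

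**1. What the change contrast removes.** Let the communities differ by a constant C at every visit, by a drift D in change from baseline, and let the programme add E to change. The group difference in change is then (C + D + E) − C = D + E. The stable difference cancels. Drift and programme effect appear only as a sum, and with one community per arm no model can split them.

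**2. Size of the drift problem.** With 75 per arm the standard error of a difference in mean change is √(2/75) = 0.163 SD of change. For a true shift δ and no programme effect, the chance of p<0.05 is 1 − Φ(1.96 − δ/0.163) + Φ(−1.96 − δ/0.163).

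| Assumed drift (SD of change) | δ/SE | False significance |
|---|---|---|
| 0 | 0 | 5% |
| 0.1 | 0.61 | 9% |
| 0.2 | 1.22 | 23% |
| 0.3 | 1.84 | 45% |

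**3. Size of the imbalance problem.** A baseline characteristic that differs by Δ SD between arms and correlates r with change shifts the unadjusted contrast by r × Δ. The same formula applies.

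| Δ | r | Shift | Unadjusted |
|---|---|---|---|
| 0.25 | 0.2 | 0.050 | 6% |
| 0.25 | 0.3 | 0.075 | 7% |
| 0.5 | 0.2 | 0.100 | 9% |
| 0.5 | 0.3 | 0.150 | 15% |

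Simulation of the same four cases gives 5.0 to 5.2% once the characteristic is in the model.

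**4. The error term.** The cancellation in step 1 gives a valid test only if the model recognises that the three visits belong to one person. Take a within-person correlation of 0.5 and no community or programme effect, and treat the data as 150 × 3 = 450 independent rows.
- Group term: the true variance of a person's three-visit mean is (1 + 2 × 0.5)/3 = 0.667, but the analysis assumes 1/3, a ratio of 2. False significance is 2[1 − Φ(1.96/√2)], or 16 to 17%.
- Group-by-time: the true error variance is 1 − 0.5 = 0.5, but the analysis uses 1. With a critical F of 3.02, the rate is about exp(−3.02/0.5) = 0.24%; simulation gives about 0.3%. The test is then far too conservative.
- With within-person error, both terms reject in about 5%.

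**5. Power cost of adjustment.** Assume a 0.5 SD effect on change. Unadjusted power is 86%. Three covariates that are balanced and unrelated to change cost almost nothing (86.04% to 86.03%). If three independent covariates are each imbalanced by Δ, variance inflates by 1 + 3Δ²/4.
- Δ = 0.25: inflation 1.05; power 84% if the covariates explain no variance, 88% if they explain 9%.
- Δ = 0.5: inflation 1.19; power 80% and 83% respectively.

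**The case against.** **The intended term is clear enough.** Two arms at three visits, an outcome worded as change, and hypotheses of greater improvement all point to group-by-time. That is right, and it is the reading used here. It does not answer steps 2 and 3, which apply to that very term, or step 4, since the SAP does not say how repeated visits are handled.

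**The arms are made comparable by design.** Shared eligibility criteria and a similar recruitment procedure do narrow the differences. They do not equalise who volunteers in each community or how each community changes over time.

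**Adjustment cannot rescue one community per arm.** True. Adjustment reduces measured imbalance only, and nothing in the documents shows that age, sex or health literacy predicts change. This is why the stated limit on interpretation matters more than the covariates.

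**This is a pilot and feasibility study.** The labels lower the stakes, and the SAP's test covers survey measures although the protocol's statement of purpose also names biomarkers. But the plan sets directional between-group hypotheses and a significance threshold, and neither label tells a reader how far the result may be taken.

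**Conclusion.** The concern holds and should be fixed. Read naturally and analysed with within-person error, the test is protected against stable differences between the two communities. It is not protected against imbalance in baseline predictors of change, a modest problem (6 to 15% false significance under the assumptions shown), nor against community-specific drift, which is potentially larger (about 9, 23 and 45% at 0.1, 0.2 and 0.3 SD) and cannot be analysed away. These figures illustrate sensitivity. The documents give no evidence on how large either problem is here.

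A reader might infer something stronger: that the group main effect will decide, so any standing difference between the communities becomes a finding. On that reading, with correlation 0.5, the SD of a person's three-visit mean is √0.667 = 0.816, and stable differences of 0.1, 0.2 and 0.3 SD would give false significance in 12, 32 and 61%. The SAP's silence permits this, but its emphasis on change and the protocol's on improvement point away from it, so these figures do not measure the plan as most naturally read. Nor do the documents show that the communities actually differ. They show only that the plan could not tell such a difference from a programme effect.

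**What to change.** Change the SAP as follows.

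1. Replace the wording that participants are divided with a statement that groups are non-randomised and defined by community of recruitment.
2. Name the tested effect as group-by-time, meaning the group difference in change from baseline at 4 and 8 months. Estimate it in a repeated-measures or mixed model that accounts for within-person correlation.
3. Adjust that contrast for a short prespecified list of baseline characteristics already collected, and present a baseline comparability table. Age and sex from the survey demographics are candidates. Baseline Newest Vital Sign score is another if it is collected in both arms: Study Design says so, but the measurement lists in Data Collection and in Research Materials, Records and Privacy omit it, and these should be reconciled first.
4. State that community and programme effects cannot be separated in this design, and that results will be reported as associations.

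Items 1, 2 and 4 need SAP wording only. Item 3 needs no new data if the health literacy score is confirmed for both arms. The costs are a more modest conclusion and possibly some power. At the assumed 0.5 SD effect, power moves from 86% to about 84 to 88% with three covariates each imbalanced by 0.25 SD, or to about 80 to 83% at 0.5 SD, depending on how much variance they explain.

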Research Materials, Records and Privacy: Identify the sources of research material obtained from individually identifiable living human subjects. Indicate what information (specimens, records, data, genetic information, etc.) will be recorded and whether use will be made of existing specimens, records or data. Explain why this information is needed to conduct the study.

Return of Research Results or Incidental Findings (if applicable):

If research has the potential to identify individual results or discover incidental findings that could affect the health of a subject, describe plans to assess, manage, and if applicable disclose findings with individual subjects or provide justification for not disclosing. For IRB expectations, refer to the UK IRB "Frequently Asked Questions (FAQs) on the Return of Research Results or Incidental Research Findings" [\[PDF\]](#).

Participants will be asked to fill out three surveys following IRB approval (May 2018, October 2018, February 2019). The surveys contain questions about demographics, self-reported health, physical activity, fruit and vegetable consumption, and community engagement. During the Farmer's Market season, walking group participants will be asked to complete weekly shopping cards that will require them to mark which fruits and vegetables they purchased at the farmer's market and how they used the fruits and vegetables they purchased at the previous market. After the Farmer's Market season, walking group participants will be asked to complete meal evaluations assessing the acceptability of the meal they received the previous week. Participants will be asked for finger-stick total cholesterol, LDL, HDL, triglycerides, hemoglobin A1c (cardio check meter), height, weight, waist circumference, blood pressure, and carotenoid status (carotenoid RS, which is a non-invasive instrument that is a reliable indicator of fruit and vegetable intake) three times (May 2018, October 2018, February 2019). The collected data will be collated and summarized without identification or attribution to the individual participants. All reports will only reveal aggregated summaries across participants. The surveys with attached consent forms will be collected and stored separately in a locked drawer in the PI's locked office at 209C

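### The SAP names no Aim 2 measure as an outcome, and its ANOVA on change in all participants neither tests the maintenance hypotheses nor restricts the improvement hypotheses to their target group

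*Combined protocol and SAP*

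**What the plan says.** **SAP.** The Statistical Analysis Plan section is three sentences long. It plans about 150 participants in walking and non-walking groups, then says "Outcomes will compare the change in fruit and vegetable intake, health and exercise at baseline, 4 months and 8 months using survey metrics", then gives a two-way ANOVA with Tukey post-hoc tests at p<0.05. It does not name the two factors and defines no subgroup, cut-off or yes/no endpoint.

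**Objectives.** Aim 1 covers physical activity and fruit and vegetable (F/V) intake. Aim 2 covers "anthropometric (weight and waist circumference) and biological (blood pressure (BP), HbA1c, and lipids) chronic disease risk factors". Each aim has two hypotheses, split by baseline status:

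- Hypothesis 1 (H1) concerns people already meeting national recommendations (Aim 1) or within normal ranges (Aim 2). Walkers "will be more likely to maintain these at 4 and 8 months than participants in the control group" for Aim 1, and "will be more likely to maintain these ranges throughout the period of the study than participants in the control group" for Aim 2.
- Hypothesis 2 (H2) concerns people who are not at those levels. It predicts greater gains in activity and F/V intake for Aim 1. For Aim 2, walkers "will have greater improvement in these measures at 4 and 8 months than participants in the control group".

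**Data sources.** Research Materials, Records and Privacy says "The surveys contain questions about demographics, self-reported health, physical activity, fruit and vegetable consumption, and community engagement". The same section lists separately "finger-stick total cholesterol, LDL, HDL, triglycerides, hemoglobin A1c (cardio check meter), height, weight, waist circumference, blood pressure, and carotenoid status". It says the data will show whether the programme "improves physical activity, fruit and vegetable intake, community engagement, group cohesion, and chronic disease-related biomarkers". Study Design and Data Collection also keep surveys and measurements apart, and plan both for both arms at three rounds.

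**The concern.** The stated analysis does not line up with the stated hypotheses in three places.

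- One of the two aims has no named outcome in the SAP.
- H1 under each aim is about the probability of a yes/no status within a group defined at baseline. The SAP compares change and defines neither the status nor the group.
- H2 under each aim is about a baseline-defined group. The SAP analyses everyone together.

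Followed as written, both maintenance hypotheses go untested. Any Aim 2 result would rest on a model, a choice of measure and cut-offs that were not stated beforehand. The H2 comparison would mix the people the hypothesis is about with those it is not about.

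**Working it through.** **Step 1. The plan's own figure.** 75 walkers + 75 controls = 150, which agrees with the SAP. The documents give no power, effect size, standard deviation (SD), event rate or dropout, so there is no sample-size calculation to reproduce.

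**Step 2. Outcomes side by side.**

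| Outcome | Where hypothesised | Source in both arms | Named in SAP |
|---|---|---|---|
| F/V intake | Aim 1 | Survey | Yes |
| Physical activity | Aim 1 | Survey | Yes, as exercise |
| Weight, waist, BP, HbA1c, lipids | Aim 2 | Measured | No |
| Carotenoid status | Opening background section | Measured | No |
| Community engagement | Opening background section | Survey | No |

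That is 0 of 5 Aim 2 outcome groups named. Itemised, they are 9 measures: weight, waist, systolic and diastolic BP, HbA1c and four lipids. Group cohesion is left out of the table because Study Design assesses social cohesion through interviews and focus groups with walkers.

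**Step 3. H1: mean change and maintenance are different quantities.** Illustration with assumed values in SD units: half of each arm is in range, in-range people sit 0.5 inside the cut-off, and the SD of change is 0.5.

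- Arm A changes by 0 in both strata. Overall mean change is 0.5 × 0 + 0.5 × 0 = 0. Maintenance is P(change > −0.5) = Φ(0.5/0.5) = 0.84.
- Arm B changes by −0.5 in range and +0.5 out of range. Overall mean change is 0.5 × (−0.5) + 0.5 × 0.5 = 0. Maintenance is Φ(0/0.5) = 0.50.

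A comparison of mean change in all participants sees no difference, while maintenance is 0.84 against 0.50.

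**Step 4. H2: what the all-participant contrast estimates.** Let f be the share not at recommended or normal levels at baseline, taken as equal in both arms. Let d be the effect in that stratum and e the effect in the other. The contrast is f·d + (1 − f)·e. The shares below are assumed, as the documents give none.

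| Effect in the other stratum | f = 20% | f = 50% | f = 80% |
|---|---|---|---|
| e = d | 100% of d | 100% | 100% |
| e = d/2 | 0.2 + 0.8 × 0.5 = 60% | 0.5 + 0.5 × 0.5 = 75% | 0.8 + 0.2 × 0.5 = 90% |
| e = 0 | 20% | 50% | 80% |

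**Step 5. Precision of an H1 comparison.** The unadjusted 95% half-width is 1.96 × √(2 × 0.7 × 0.3 / n per arm), with 70% maintained in both arms (assumed).

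| In range at baseline (assumed) | No dropout | 20% dropout (assumed) |
|---|---|---|
| 80% | n = 60: 16 points | n = 48: 18 points |
| 50% | n = 37.5: 21 points | n = 30: 23 points |
| 20% | n = 15: 33 points | n = 12: 37 points |

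In the 20% row there are 30 people in total and 30 × 0.3 = 9 non-maintainers. With dropout it is 24 × 0.3 ≈ 7.

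**Step 6. Number of comparisons, classified measure by measure.** Aim 1: 2 outcomes × (H1 at 2 visits + H2 at 2 visits) = 8. Aim 2: 9 measures × (H1 once + H2 at 2 visits) = 27. The sum is 35. Carotenoid status and community engagement at 2 visits each add 4, giving 39. Self-reported health at 2 visits adds 2, giving 41. With no true effects, 41 × 0.05 = 2.05 false positives are expected.

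**The case against.** **Health may be shorthand for Aim 2.** This is possible and cannot be ruled out. It does not rescue the plan, because no measure is named and the sentence ties the word to the survey. A reader might go further and infer that Aim 2 has been dropped. The documents do not support that: every Aim 2 measure is collected in both arms at three rounds.

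**An ANOVA can compare improvement.** This stands. If the unnamed factors are group and time, the ANOVA compares mean change, which is the right kind of quantity for H2. It would be wrong to infer that the method is invalid for H2; what is missing is the restriction by baseline status. Likewise, an ANOVA on a 0/1 maintenance indicator among people in range would be a crude test of H1, but the SAP does not specify one.

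**The dilution may be small.** This also stands. A loss down to 20% of the effect requires no effect at all in people already at recommended or normal levels, and H1 predicts some benefit there. The last row of Step 4 is a bound under assumed shares and not a forecast.

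**Baseline status could be read jointly.** Objectives could mean all measures together and not each one separately. People of mixed status would then fall outside both strata, and the counts in Step 6 would change. The measure-by-measure reading is a choice, and the SAP should state it.

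**It is a pilot in a convenience sample.** The opening background section and Study Design say it is a feasibility study and a pilot. This lowers the severity. It does not remove the mismatch between hypotheses and analysis.

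**Conclusion.** The concern holds for the SAP as written. None of the 5 Aim 2 outcome groups is named, neither of the 2 maintenance hypotheses has a test, and neither of the 2 improvement hypotheses has its baseline restriction. These counts come from the text and need no assumption. The size of any bias in H2 depends on two things that the documents do not give: the share of participants in each stratum and the effect in the other stratum. It ranges from none, if the effects are equal, to the bound in Step 4.

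This should be fixed before analysis. A reader might infer that it invalidates the study, but the results will be exploratory and nothing planned for collection is lost.

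**What to change.** 1. **Outcomes.** Limit the survey-metrics wording to F/V intake, physical activity, self-reported health and community engagement. Do not strike it altogether: pedometer and shopping-card data exist only for walkers, so the survey is the SAP's between-arm source for Aim 1. Add weight, waist circumference, systolic and diastolic BP, HbA1c, each lipid and carotenoid status as measured outcomes.
2. **Definitions.** Before analysis, fix the cut-offs for national recommendations and normal ranges; the documents supplied give none. State that baseline status is classified measure by measure.
3. **H2.** Among people not meeting recommendations or out of range at baseline, compare change at 4 and 8 months between groups with a repeated-measures model adjusted for the baseline value. Show the all-participant difference beside it.
4. **H1.** Among people meeting recommendations or in range at baseline, compare the proportion maintained as a risk difference with 95% CI. Use 4 and 8 months for Aim 1. For Aim 2, use in range at both follow-up visits, and state this as the working definition of maintenance throughout the study. Adjust for the baseline value and a short pre-named list of demographics only where the number of non-maintainers allows. Otherwise report the unadjusted difference.
5. **Interpretation.** Note that the arms are two non-randomised counties, and label all results exploratory.

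The cost is SAP wording and added analysis, using only data already planned. There are two downsides. Intervals will be wide in small strata, and about 9 non-maintainers (Step 5, 20% row) would not support an adjusted model. There will also be many comparisons (Step 6), which is a further reason for the exploratory label.
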